15.3. Appendix 3: Assessment Windows

15.3.1. Definitions of Assessment Windows for Analyses

Analysis Set / Domain	Parameter (if applicable)	Target	Analysis tin Window	Analysis Timepoint	
		timepoin t	Earliest Timepoint	Latest Timepoint	
ITT/PP	V_{T}	30 mins	20 mins	60 mins	Day 1
ITT/PP	SUV	30 mins	20 mins	60 mins	Day 1
ITT/PP	V_{T}	24 hours	14 hours	28 hours	Day 2
ITT/PP	SUV	24 hours	14 hours	28 hours	Day 2

15.4. Appendix 4: Study Phases and Treatment Emergent Adverse Events

15.4.1. Study Phases

Assessments and events will be classified according to the time of occurrence relative to study treatment.

Study Phase	Definition
Pre-Treatment	Date ≤ Study Treatment Start Date
On-Treatment	Study Treatment Start Date < Date ≤ Study Treatment Stop Date + 1
Post- Treatment	Date > Study Treatment Stop Date + 1

15.4.1.1. Study Phases for Concomitant Medication

Study Phase	Definition
Prior	If medication end date is not missing and is before 7 days prior to screening visit
Concomitant	Any medication that is not a prior

NOTES:

Please refer to Appendix 7: Reporting Standards for Missing Data for handling of missing and partial
dates for concomitant medication. Use the rules in this table if concomitant medication date is
completely missing.

15.4.2. Treatment Emergent Flag for Adverse Events

Flag	Definition
Treatment Emergent	 If AE onset date is on or after treatment start date & on or before treatment stop date. Study Treatment Start Date ≤ AE Start Date ≤ Study Treatment Stop Date +1 For studies with greater than one treatment period (e.g., Period 1 and Period 2), if AE onset is during one period and worsens during a later period it would be counted in both periods. For the initial period the logic would be as above. For the later period the logic would use the treatment dates associated with the later period: Treatment Period Start Date ≤ AE Worsening Date ≤ Study Treatment Stop Date + 1

NOTES:

- If the study treatment stop date is missing, then the AE will be considered to be On-Treatment.
- Time of study treatment dosing and start/stop time of AEs should be considered, if collected.

15.4.3. Categorisation of adverse events into Dosing Periods

AEs will be categorised into 4 groups (Dosing Period 1, Dosing Period 1 follow up, Dosing Period 2 and Dosing Period 2 follow up) as shown in table below. AEs are assigned up to 72 hours for the dosing periods as GSK3008348 will be expected to have cleared the systemic circulation by 72 hours [GSK3008348 has a half-life of 8-10 hours and so 72 hours >5 half-lives]. Any AEs prior to dosing will be listed as screening AEs and will not be summarised.

Dosing Period 1	Start of first dose GSK3008348 to 72 hrs post start of dose
Dosing Period 1 Follow up (which will include washout and baseline scan)	72 hours post start of first dose of GSK3008348 (Period 1) to start of second dose of GSK3008348 (Period 2), or end of study follow up for subjects that were withdrawn before dosing period 2
Dosing Period 2	Start of second dose GSK3008348 to 72 hrs post start of second dose
Dosing Period 2 Follow up	72 hours post start of second dose of GSK3008348 (Period 2) to end of follow up for the study.

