- Dosing period 1: participants will have pre-dose health assessments and a pharmacogenetics sample at the clinical unit on the morning of Day 1. They will remain in the clinical unit for at least 8 h after receiving their nebulised dose for safety observations, and then return to the clinical unit on Day 2. Safety assessments will be done, and PK and exploratory biomarker samples taken.
- Baseline PET scan and HRCT scan at least 7 days after the first dose, and a maximum of 14 days before the first post-dose PET scan.
- Dosing period 2: participants will attend the clinical unit for health assessments before dosing, on Day 1 or Day –1. If participants pass the health assessments, they will attend the imaging unit, have their dose administered, and have up to 2 post-dose PET scans. Alternatively, dosing may take place at the clinical unit before the patient is transferred to the imaging unit for their PET scan, depending on the PET scan timing; however, the participant must be observed for at least 4 h post-dose without changing location. The timing of the post-dose PET scans will be determined based on emerging study data. Doses will be separated by a washout of between 7 and 28 days.

### 5.1.3. Changes to Cohorts 1 or 2

Participants in Cohorts 1 and 2 will have 2 planned dosing periods. However, if a PET scan cannot be performed (e.g. because of technical issues, PET ligand synthesis radiochemistry failure, or because the participant cannot be scanned for safety reasons), participants may repeat the visit or dosing period, and repeat procedures in order to

obtain a full dataset for each endpoint. Participants may be administered an additional dose of GSK3008348 after a 7-day washout, such that they receive a maximum of 3 single doses in total during the study. Participants will not, however, be administered an additional dose of [F]-FBA-A20FMDV2; they will receive a maximum of 3 doses of the radiotracer during the study.

If a participant experiences unexpected and/or potentially serious side effects after their first or second dose, they will be referred to the clinical site investigator for assessment and ongoing care. That may include admission to a clinical bed, if deemed appropriate by the investigator, as per routine clinical practice.

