15.10.5. Safety Tables

Safety: Ta	ables				
No.	Population	IDSL / Example Shell	Title	Programming Notes	Deliverable [Priority]
Adverse F	Events (AEs)				
2.1.	ITT	AE1	Summary of All Adverse Events by System Organ Class and Preferred Term	ICH E3, Overall and by Dosing period (Dosing Period 1, Dosing Period 1 follow up, Dosing Period 2 and Dosing Period 2 follow up)	SAC
2.2.	ITT	AE1	Summary All Drug-Related Adverse Events by System Organ Class and Preferred Term	ICH E3, Overall and by Dosing period (Dosing Period 1, Dosing Period 1 follow up, Dosing Period 2 and Dosing Period 2 follow up) As 2.1 notes	SAC
Laborator	ry: Chemistry	,		1	ı

Safety: Ta	Safety: Tables					
No.	Population	IDSL / Example Shell	Title	Programming Notes	Deliverable [Priority]	
2.3.	ITT	LB1	Summary of Chemistry Changes from Baseline	ICH E3, By treatment and by Dosing period (Period 1, Period 2) Includes Baseline values. Includes pre-specified parameters repeated in conventional units.	SAC	
Laborator	y: Hematolog	gy				
2.4.	ITT	LB1	Summary of Hematology Changes from Baseline	ICH E3, By treatment and by Dosing period (Period 1, Period 2) Includes baseline values.	SAC	
Laborator	y: Urinalysis					
2.5.	ITT	UR3b	Summary of Urinalysis Dipstick Results by Planned Timepoint	ICH E3, By treatment and by Dosing period (Period 1, Period 2) Includes Baseline values.	SAC	
ECG						

Safety: Ta	Safety: Tables					
No.	Population	IDSL / Example Shell	Title	Programming Notes	Deliverable [Priority]	
2.6. ITT			IDSL, By treatment and by Dosing period (Period 1, Period 2)			
	ITT	ITT EG1	Summary of ECG Findings	As above for Chemistry, using ECG findings categories (and change from baseline categories, if applicable).	SAC	
2.7.	ITT	EG2	Summary of Change from Baseline in ECG Values by Visit	IDSL, By treatment and by Dosing period (Period 1, Period 2) Includes Baseline values.	SAC	

Safety: Ta	bles				
No.	Population	IDSL / Example Shell	Title	Programming Notes	Deliverable [Priority]
Vital Sign	s				
2.8.	ITT	VS1	Summary of Change from Baseline in Vital Signs	ICH E3, By treatment and by Dosing period (Period 1, Period 2) Includes Baseline values.	SAC
Lung Fun	ction Tests: (1	FEV1, % Predicted	FEV ₁ , FVC and % Predicted FVC)		
2.9.	ITT	PFT1	Summary of Pulmonary Function Test Data	Absolute and % Predicted, by Visit	SAC
2.10.	ITT	PFT3	Summary of Change from Baseline Pulmonary Function Test Data	Absolute and % Predicted, by Visit	SAC

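### The SAP's adverse-event periods have no on-dose window for the third dose that the protocol permits, so the by-period split would misplace any events that follow one

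*SAP*

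**What the plan says.** SAP 15.4.3 states: "AEs will be categorised into 4 groups (Dosing Period 1, Dosing Period 1 follow up, Dosing Period 2 and Dosing Period 2 follow up"). Dosing Period 2 is defined as "Start of second dose GSK3008348 to 72 hrs post start of second dose". The group after it is defined as "72 hours post start of second dose of GSK3008348 (Period 2) to end of follow up for the study". The 72 h limit is justified pharmacokinetically: "GSK3008348 will be expected to have cleared the systemic circulation by 72 hours", because "GSK3008348 has a half-life of 8-10 hours and so 72 hours >5 half-lives". SAP 15.10.5 applies these groups to the two adverse-event summary tables, 2.1 (all events) and 2.2 (drug-related events), each of which is to be shown "Overall and by Dosing period (Dosing Period 1, Dosing Period 1 follow up, Dosing Period 2 and Dosing Period 2 follow up").

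Protocol 5.1.3 describes two planned dosing periods and then a contingency. If a PET scan cannot be performed, "participants may repeat the visit or dosing period, and repeat procedures in order to" complete the dataset. It continues: "Participants may be administered an additional dose of GSK3008348 after a 7-day washout, such that they receive a maximum of 3 single doses". Protocol 9.6 repeats this, giving a failed quality check on the tracer after dosing as an example. The protocol synopsis times the follow-up visit at 7–14 days after the final dose, so study follow-up extends past a third dose. The SAP has no rule for assigning events after a third or repeat dose.

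**The concern.** The SAP's reasoning makes the dosing-period columns stand for time on drug and the follow-up columns for time after clearance. A third dose would break that. An event starting minutes after it would be counted in a column meant for time after the drug has cleared.

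The split matters because safety and tolerability is a primary objective (Protocol 4). Local irritancy is the one risk listed under the investigational product in Protocol 3.3.1. That section expects irritancy symptoms to be acute and relies on this to tell them apart from chronic IPF symptoms such as cough and dyspnoea. Timing relative to dose is therefore part of how these events are to be read, and Tables 2.1 and 2.2 are the only adverse-event summary tables that display it.

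**Working it through.** **Inputs**

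- Half-life 8–10 h, and a 72 h window from the start of a dose: SAP 15.4.3.
- Minimum washout before an additional dose 7 days, maximum three doses: Protocol 5.1.3.
- Follow-up visit 7–14 days after the final dose: Protocol synopsis.
- Five active participants planned in Cohort 1: Protocol 5.1.1 (7 randomised 5:2).

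**Step 1. The SAP's own figure.** Five half-lives are 5 × 8 = 40 h to 5 × 10 = 50 h, both below 72 h. Put the other way, 72/10 = 7.2 and 72/8 = 9.0 half-lives. The statement that 72 h exceeds five half-lives reproduces.

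**Step 2. Position of a third dose.** Set time zero at the start of the second dose.

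| Event | Hours after second dose |
|---|---|
| Dosing Period 2 window closes | 72 |
| Earliest third dose, 7 × 24 | 168 |
| Third dose + 72 h | 168 + 72 = 240 |
| Follow-up visit, 7 to 14 days after third dose | 168 + 168 = 336 to 168 + 336 = 504 |

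The third dose comes at least 168 − 72 = 96 h after Dosing Period 2 has closed. A longer washout only widens that gap.

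**Step 3. Apply the rule as written.** Every hour from 168 to 240 is later than 72 h after the second dose and earlier than the end of follow-up. All of it falls in *Dosing Period 2 follow up* and none in a dosing period. For a participant given three doses, one dose in three has no on-dose window.

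**Step 4. With windows anchored to each dose.** Hours 168–240 become an on-dose period. Follow-up then consists of 72–168 h and 240 h to the end of follow-up (336–504 h).

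**Step 5. Size in a table.** Suppose one active participant has such an event and is not otherwise counted for that term in the affected column. With 5 active participants in the ITT population the column's incidence moves by 1/5 = 20 percentage points. With 6 it moves by 1/6 = 16.7 points. Six is included because replacements are allowed (Protocol 5.2) and SAP Listing 35 mentions an extra ITT participant with baseline PET data only, whose arm is not stated.

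**The case against.** The strongest reply is that nothing may have gone wrong. The third dose is a contingency, and neither document reports one. The SAP amendment was written after the interim analysis (SAP 1.1), when five active participants had completed dosing period 2 with valid baseline and 30-minute scans (SAP 3.1), and Cohort 2 had been dropped. The authors may have kept four groups because there was no third dose to classify. That is plausible and stands as a limit on the consequence. It remains inference, because the SAP does not say so. For the same reason, the amendment's timing is not evidence of an oversight that affected results.

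A reader might also infer that adverse events after a third dose would be lost, or that the study's adverse-event counts would be understated. The documents do not support that. Tables 2.1 and 2.2 also have an overall display, which keeps every event. Listing 13 (all adverse events) and Listing 12 (exposure) let a reader trace an event to a dose. The treatment-emergent flag in SAP 15.4.2 runs on treatment start and stop dates, so it would cover a third dose provided the stop date is that of the last dose. No formal safety comparison is planned (SAP 2.4), and the period rule is the same in both arms.

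Finally, a repeated dosing period could be read as still being Period 2, so that a programmer would place its events there. The SAP text is anchored to the second dose, so this needs an unwritten rule. It also does not close the gap alone: if Period 2 is taken to begin at the third dose, events after the second dose fall into *Dosing Period 1 follow up*. One of the three doses still lacks a window unless the SAP says that both belong to Period 2.

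**Conclusion.** The point holds as a conditional defect in a stated rule. In a situation that the protocol expressly permits, SAP 15.4.3 assigns the whole 72 h after a third dose to follow-up, against its own clearance rationale.

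The damage is confined to the by-period columns of Tables 2.1 and 2.2. It is nil if no third dose was given. If one was, each affected event could move a period-specific active-arm incidence by about 17–20 percentage points, assuming 6 or 5 active ITT participants and that the participant is not already counted for that term in the column. The documents do not support concluding that events were in fact misclassified, or that the overall safety picture is wrong. The correction is still worth making before the final tables, because it is cheap and the split serves a primary objective.

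**What to change.** In SAP 15.4.3, define the windows by dose administered. Each on-dose window runs from the start of a dose to 72 h after it. Each follow-up window runs from 72 h after that dose to the start of the next dose, or to the end of study follow-up if there is none. State whether the 72 h after a repeat dose is pooled with Dosing Period 2 or shown as a separate repeat-dose category with its own follow-up, and carry that choice into Tables 2.1 and 2.2. If no participant received a third dose, one sentence in the SAP saying so closes the point.

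The cost is a wording change and one derivation. Protocol 7.6 already requires the date and time of each dose to be recorded, so no new data are needed. The change affects tabulation only and does not touch dosing or clinical management.

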15.5. Appendix 5: Data Display Standards & Handling Conventions

All displays (Tables, Figures & Listings) will use the term 'Subjects'. However, RAP text will refer to "Participants" in-line with the master RAP template and protocol.

15.5.1. Reporting Process

Software					
• The currently s	The currently supported versions of SAS software will be used.				
Reporting Area					
HARP Server	: uk1salx00175				
HARP Area	:\arprod\gsk3008348\mid204715\internal_01				
Interim					
HARP Area Dry-	:\arprod\gsk3008348\mid204715\data_look_01				
run					
HARP Area SAC	:\arprod\gsk3008348\mid204715\final_01				
QC Spreadsheet	: \arwork\gsk3008348\mid204715\ internal_01\Documents				
QC Spreadsheet	: \arwork\gsk3008348\mid204715\final_01\Documents				
QC Spreadsheet	:\arwork\gsk3008348\mid204715\data_look_01\documents				
Analysis Datasets					

Analysis Datasets

 Analysis datasets were created according to Legacy GSK A&R dataset standards (IDSL) for the interim analyses in Cohort 1. The same standards will be used for the final analyses.

Generation of RTF Files

• RTF files were generated for tables and figures for the IA. In addition, pdf files of the plots were generated at IA. Similarly, RTF files for tables and pdf files of the plots will be generated at Statistical Analysis Complete (SAC) reporting effort.

15.5.2. Reporting Standards

General

- The current GSK Integrated Data Standards Library (IDSL) will be applied for reporting, unless otherwise stated (IDSL Standards Location: https://spope.gsk.com/sites/IDSLLibrary/SitePages/Home.aspx):
 - 4.03 to 4.23: General Principles
 - 5.01 to 5.08: Principles Related to Data Listings
 - 6.01 to 6.11: Principles Related to Summary Tables
 - 7.01 to 7.13: Principles Related to Graphics
- Do not include subject level listings in the main body of the GSK Clinical Study Report. All subject level listings should be in the modular appendices as ICH or non-ICH listings

Formats

• GSK IDSL Statistical Principles (5.03 & 6.06.3) for decimal places (DP's) will be adopted for reporting of data based on the raw data collected, unless otherwise stated.

- Numeric data will be reported at the precision collected on the eCRF.
- The reported precision from non eCRF sources will follow the IDSL statistical principles but may be adjusted to a clinically interpretable number of DP's.

Planned and Actual Time

- Reporting for tables, figures and formal statistical analyses:
 - Planned time relative to dosing will be used in figures, summaries, statistical analyses and calculation of any derived parameters, unless otherwise stated.
 - The impact of any major deviation from the planned assessment times and/or scheduled visit days on the analyses and interpretation of the results will be assessed as appropriate.
- Reporting for Data Listings:
 - Planned and actual time relative to study drug dosing will be shown in listings (Refer to IDSL Statistical Principle 5.05.1).
 - Unscheduled or unplanned readings will be presented within the subject's listings.

Unscheduled Visits

- Unscheduled visits will not be included in summary tables and/or figures.
- All unscheduled visits will be included in listings.

Descriptive Summary Statistics Continuous Data Refer to IDSL Statistical Principle 6.06.1 Categorical Data N, n, frequency, % Graphical Displays

• Refer to IDSL Statistical Principals 7.01 to 7.13.

15.5.3. Reporting Standards for Pharmacokinetic

Pharmacokinetic C	Pharmacokinetic Concentration Data				
PC Windows Non- Linear (WNL) File	PC WNL file (CSV format) for the non-compartmental analysis by Clinical Pharmacology Modelling and Simulation function will be created according to Standards for the Transfer and Reporting of PK Data using HARP. Note: Concentration values will be imputed as per GUI_51487				
Descriptive Summary Statistics, Graphical Displays and Listings	Refer to IDSL PK Display Standards. Refer to IDSL Statistical Principle 6.06.1. Note: Concentration values will be imputed as per GUI_51487 for descriptive summary statistics/analysis and summarized graphical displays only.				
NONMEM/Pop PK File	Pop-PK file (CSV format) for the POP-PK analysis by Clinical Pharmacology Modelling and Simulation function maybe created if appropriate. The data specification and timeline for creation of this file will be independent of the analysis described in this RAP. In an event that GSK3008348 is terminated before these analyses are conducted, this file will not be created.				
NONMEM/PK/PD File	PK/PD file (CSV format) for the PK/PD analysis by Clinical Pharmacology Modelling and Simulation function maybe created, if				

	appropriate. The data specification and timeline for creation of this
	file will be independent of the analysis described in this RAP. In an
	event that GSK3008348 is terminated before these analyses are
	conducted, this file will not be created.
Pharmacokinetic P	arameter Derivation
PK Parameter to	AUC _(0-t) /D, AUC _(0-inf) /D and C _{max} /D
be Derived by	
Programmer	
Pharmacokinetic P	arameter Data
Is NQ impacted	Yes, refer to Standards for Handling NQ Impacted PK Parameters.
PK Parameters	
Rule Being	
Followed	
Descriptive	Refer to IDSL PK Display Standards.
Summary	
Statistics,	
Graphical	
Displays and	
Listings	

15.6. Appendix 6: Derived and Transformed Data

15.6.1. General

Multiple Measurements at One Analysis Time Point

- Mean of the measurements will be calculated and used in any derivation of summary statistics but if listed, all data will be presented.
- If there are two values within a time window (as per Section 15.3.1) the value closest to the target day for that window will be used. If values are the same distance from the target, then the mean will be taken.
- Participants having both High and Low values for Normal Ranges at any post-baseline visit for safety parameters will be counted in both the High and Low categories of "Any visit post-baseline" row of related summary tables. This will also be applicable to relevant Potential Clinical Importance summary tables.

Study Day

- Calculated as the number of days from First Dose Date within a treatment period:
 - \circ Ref Date = Missing \rightarrow Study Day = Missing
 - o Ref Date < First Dose Date → Study Day = Ref Date First Dose Date
 - o Ref Data \geq First Dose Date \rightarrow Study Day = Ref Date (First Dose Date) + 1

15.6.2. Safety

ECG Parameters

RR Interval

• ECGs are machine read, the RR value preceding the measurement QT interval was only collected during Imanova visits. Missing RR interval (msec) will not be derived.

Corrected QT Intervals

- When not entered directly in the eCRF, corrected QT intervals by Bazett's (QTcB) and Fridericia's (QTcF) formulas will be calculated, in msec, depending on the availability of other measurements.
- If RR interval (msec) is provided then missing QTcB and/or QTcF will be derived as:

$$QTcB = \frac{QT}{\sqrt{\frac{RR}{1000}}} \qquad \qquad QTcF = \frac{QT}{3\sqrt{\frac{RR}{1000}}}$$

Laboratory Parameters

- If a laboratory value which is expected to have a numeric value for summary purposes, has a non-detectable level reported in the database, where the numeric value is missing or replaced with a character value starting with '<x' or '>x' (or indicated as less than x or greater than x in the comment field), the number of significant digits in the observed values will be used to determine how much to add or subtract in order to impute the corresponding numeric value.
 - o Example 1: 2 Significant Digits = '< x' becomes x 0.01
 - o Example 2: 1 Significant Digit = '> x' becomes x + 0.1
 - Example 3: 0 Significant Digits = < x' becomes x 1.
- If there is more than one value of a particular parameter for a subject for a visit, the scheduled value will be used in summary statistics; all values will be listed.

15.6.3. Pharmacokinetic

Dose-Normalised Parameters

AUC_(0-t), AUC_(0-inf) and C_{max}

Derived as: PK parameter/ Inhaled dose (mg)

15.6.4. Pharmacodynamic

The V_T and SUV are already derived. These endpoints will be further natural log-transformed.

15.7. Appendix 7: Reporting Standards for Missing Data

15.7.1. Premature Withdrawals

Element	Reporting Detail
General	• Subject study completion is defined as a subject having reached Last Subject Last Visit (LSLV) at the end of Dosing Period 2 in Cohort 1.
	• Withdrawn subjects will be replaced in the study if they withdraw before successful completion of the 30mins PET scan in Dosing Period 2 of Cohort 1.
	All available data from participants who were withdrawn from the study will be listed and all available planned data will be included in summary tables and figures, unless otherwise specified.
	• Withdrawal visits will be slotted as per Appendix 3: Assessment Windows or will be summarised as withdrawal visits.

